5.2 Clinical Laboratory Assessments

5.2.1 Routine Assessments and Biomarkers

A list of all clinical laboratory tests that will be performed is provided in Table 4; the time points for sample collection are specified in the SOA. Central lab reference ranges will be used throughout the study, including in the event that labs are analyzed locally. All attempts should be made to draw lab samples for central lab analysis when samples are needed for local analysis.

Blood will be collected for standard hematology and serum chemistry (including coagulation parameters).

During Screening, if a subject's ALT or AST is greater than $3 \times ULN$; or a subject has elevated bilirubin or PT/INR, confirmatory testing will be completed. Confirmatory testing may be completed locally or by the central lab, however results will be based on the standardized reference ranges provided in the central laboratory manual for this study. Abnormal safety labs at Screening can be repeated within 1 to 2 weeks. The difference between these two pre-treatment values for each abnormal lab should differ by <20% in each subject.

Efforts should be made by the Investigator to review subject medical history, concomitant medications and health status so that a clear explanation for the elevation is established. The Investigator, in consultation with the Sponsor, shall make a determination of subject eligibility based on review of Exclusion Criteria #8.

During the study, after treatment with SBC-103, in the event that a subject's ALT or AST are $2 \times$ ULN (when baseline ALT or AST were within normal limits) or $3 \times$ ULN (when baseline ALT or AST was greater than $1.5 \times$ ULN), or when a subject has an elevation in bilirubin or PT/INR a confirmatory test should be completed at the earliest possible time point, but not later than the next scheduled visit. Upon positive confirmation of the elevated transaminases as described above, dosing will be paused until AST and ALT have returned to baseline or to study nadir (nadir values may be confirmed by additional lab sampling at the discretion of the investigator, using the same lab for analysis of each sample), or normalized if the baseline level was within normal limits. See Section 6.2.1 for stopping rules.

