6.2 Stopping Rules

6.2.1 Stopping Rules in Individual Subjects

During Part A (Initial Therapy), Part B (Therapy at 1 and/or 3 mg/kg), and Part C (Therapy at 5 and/or 10 mg/kg), subjects who experience a severe IAR, a serious or severe AE that is

Page 75 of 121

considered related to SBC-103, or a significant elevation in specific laboratory values will have SBC-103 dosing paused based on the rules described below.

For IARs:

- Subjects who develop a severe IAR, as defined in Section 7.1.3, must stop treatment until their information is reviewed by the SRC. Dosing with alterations to the infusion regimen (eg, pretreatment or slowing the rate of infusion) may resume once the SRC and the Sponsor approve.
- Subjects with mild or moderate IARs can continue receiving SBC-103 in the study. The SRC or Sponsor may recommend alterations to the infusion regimen (eg, pretreatment or slowing the rate of infusion).

For all other AEs (ie, AEs that are not characterized as IARs):

- Any event considered related to SBC-103 which is either serious or severe will result in pausing additional dosing in an individual subject. The SRC and the Sponsor will review the data and will resume dosing only after review and agreement.
- Subjects with mild or moderate non-serious AEs can continue receiving SBC-103 in the study.

For Laboratory Values:

- Dosing will be paused based on confirmed elevations in AST or ALT under the following circumstances:
 - In the event that a subject's AST or ALT is greater than or equal to 2 times the ULN (when baseline ALT or AST was within normal limits)
 - In the event that a subject's AST or ALT is greater than or equal to 3 times the ULN (if baseline ALT or AST greater than 1.5 ULN).

Dosing will only resume after AST or ALT have returned to baseline or to study nadir (nadir values may be confirmed by additional lab sampling at the discretion of the investigator, using the same lab for analysis of each sample), or normalized if the baseline level was within normal limits.

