The subject should be restarted at a reduced dose. For example, if a subject was receiving a dose of 10 mg/kg, he/she would be restarted at 5 mg/kg; subjects receiving 5 mg/kg would be restarted at 3 mg/kg; etc. In the event that the subject was receiving a dose of 0.3mg/kg, he/she may resume at the 0.3 mg/kg dose only after AST or ALT have returned at least to baseline or to study nadir (nadir values may be confirmed by additional lab sampling at the discretion of the investigator, using the same lab for analysis of each sample), or normalized if the baseline level was within normal limits.

If after resuming treatment at the lower dose, the ALT or AST elevation recurs at greater than or equal to 2 times the ULN (for those with ALT or AST within normal limits at baseline) or 2 times the baseline value (for those with abnormal ALT or AST at baseline) study drug should be stopped and not resumed. Dosing will be paused based on confirmed elevations in AST or ALT with accompanying elevations in the following

• Confirmed bilirubin greater than 1.5 times ULN

- Confirmed INR increase of 0.2
- Eosinophilia (more than 5%), rash or fever

If these bilirubin and INR values normalize (and the independent SRC believes that it is safe to do so), the subject may resume dosing on a lower dose of the study drug (eg, those on a 3 mg/kg would resume dosing at 1 mg/kg, those on a 0.3 mg/kg dose would resume the 0.3 mg/kg dose). However, in this scenario, if a subject develops recurrent elevations in AST or ALT (with or without elevations in total bilirubin or INR), the drug should be stopped and not resumed.

Subjects whose rise in LFTs is accompanied by eosinophilia (more than 5%), rash or fever should not be restarted on the study drug.

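### Restart after a combined ALT/AST plus bilirubin or INR rise (Protocol Section 6.2.1) states no enzyme recovery condition, so a child with both baselines above 1 and up to 1.5 x ULN has none

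*Protocol*

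**What the plan says.** Protocol Section 6.2.1, under laboratory values, contains two kinds of liver pause.

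**Enzyme-only pause.** Dosing pauses on a confirmed ALT or AST that is "greater than or equal to 2 times the ULN (when baseline ALT or AST was within normal limits"), or "greater than or equal to 3 times the ULN (if baseline ALT or AST greater than 1.5 ULN"). The restart condition comes directly after: "Dosing will only resume after AST or ALT have returned to baseline or to study nadir", or normalized if the baseline was normal. Section 5.2.1 gives the same two baseline groups and says that, once those elevations are confirmed, "dosing will be paused until AST and ALT have returned to baseline or to study nadir". Restart is at a reduced dose. If the elevation then recurs at 2 x ULN (normal baseline) or at "2 times the baseline value (for those with abnormal ALT or AST at baseline) study drug should be stopped and not resumed".

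**Combined pause.** "Dosing will be paused based on confirmed elevations in AST or ALT with accompanying elevations in the following": bilirubin above 1.5 x ULN, an INR increase of 0.2, or eosinophilia, rash or fever. No multiple is given for ALT or AST. For the bilirubin and INR form, the restart rule is "If these bilirubin and INR values normalize (and the independent SRC believes that it is safe to do so), the subject may resume dosing", with a dose reduction (a child on 0.3 mg/kg stays at 0.3). After such a restart, "if a subject develops recurrent elevations in AST or ALT (with or without elevations in total bilirubin or INR"), the drug is stopped permanently. A rise with eosinophilia, rash or fever may not be restarted at all, so it plays no part in this point.

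The SAP does not address these rules.

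**The concern.** An enzyme rise with raised bilirubin or INR is a more worrying liver signal than an enzyme rise alone. One would expect its restart rule to be at least as demanding on the enzymes. Instead it is silent on them, and the reader must borrow the recovery condition from the enzyme-only rule.

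That borrowing works only where an enzyme-only trigger has also been met. The two triggers are defined by baseline: within normal limits, or above 1.5 x ULN. A baseline above 1 and up to 1.5 x ULN is in neither group. For a child with both enzymes there, the written rules would allow re-dosing once bilirubin and INR have normalized, with ALT and AST still raised, subject to the SRC's judgement. What is at stake is re-exposing a child to a drug that may be injuring the liver before the enzymes show that the injury has settled.

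**Working it through.** No sample size or error rate is involved. The check is to apply the written rules by baseline. Let B be the baseline in multiples of ULN and P the peak.

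**Inputs.** Enzyme-only triggers: P >= 2 if B <= 1, and P >= 3 if B > 1.5 (Sections 5.2.1 and 6.2.1). The combined trigger is taken as any P above both B and ULN, since no multiple is stated. Exclusion criterion 8 (Section 4.3.2) gives ALT or AST above 3 x ULN as its example, so a baseline between 1 and 1.5 x ULN does not by itself bar enrolment.

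**Result for a combined rise, reading the rules enzyme by enzyme.**

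| Baseline B (x ULN) | Recovery condition applies from | Combined rises with no stated recovery condition |
|---|---|---|
| <= 1 | 2.0 x ULN | above 1 and below 2 x ULN |
| above 1, up to 1.5 | never | any size |
| > 1.5 | 3.0 x ULN | raised, but below 3 x ULN |

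Stepping through assumed baselines of 0.8, 1.0, 1.01, 1.2, 1.5, 1.51, 2.0 and 2.9 and assumed peaks of 1.8, 2.5, 3.5, 8 and 20 x ULN confirms the table. At B = 1.01, 1.2 and 1.5 the enzyme-only trigger is not met even at a peak of 20. At B = 1.0 it is met at 2.5, and at B = 1.51 it is met at 3.5. The edges are exact: 1.0 counts as normal, and 1.5 is not greater than 1.5.

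The first and third rows are a minor inconsistency, because the protocol does not pause for isolated enzyme rises of that size either. The middle row is the gap.

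**Which children are in the middle row.** Both triggers refer to ALT or AST at baseline. Read literally, a child with one enzyme in the band and the other normal meets the wording of the 2 x ULN rule. The gap is therefore certain only when both baselines lie in the band, or when the rule is applied separately to each enzyme.

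**Two readings of the combined trigger.**
- Any confirmed elevation: the child in the band is paused, and restart depends on bilirubin, INR and the SRC only.
- The same 2 x and 3 x ULN elevations as before: the child in the band is not paused by this rule at all, and again has no enzyme recovery condition.

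**Contrast within the section.** For a child on 0.3 mg/kg, whose dose cannot be lowered, the enzyme-only rule repeats that ALT or AST must recover before restart. The combined rule lets the same child resume at 0.3 mg/kg without saying so.

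**Scale.** After an enzyme-only pause, the permanent-stop level for an abnormal baseline is 2B: 2 x 1.1 = 2.2, 2 x 1.3 = 2.6 and 2 x 1.5 = 3.0 x ULN. Suppose ALT is still 4 x ULN when bilirubin normalizes (an assumed value). That is 4/1.1 = 3.6, 4/1.3 = 3.1 and 4/1.5 = 2.7 times baseline. These figures only give a sense of size: 2B is a recurrence level, not a restart criterion.

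**The case against.** The strongest reply is that restart is not automatic. The SRC must believe it safe, a requirement that the enzyme-only restart text does not contain. The dose normally falls. After a combined restart, a recurrent enzyme elevation stops the drug with no multiple needed, which is stricter than the enzyme-only path. A related serious or severe event separately pauses dosing until the SRC and sponsor agree. Section 7.2.4 asks for hepatologist evaluation of possible drug-induced liver injury, and Section 7.5 provides ad-hoc SRC review. Leaving the decision to expert judgement is a defensible design. All of this stands and keeps the risk small, but none of it says what ALT and AST must show before re-dosing.

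A second reply is that the recovery sentence might govern every laboratory pause, since the layout of the section is hard to reconstruct. That cannot be excluded. However, the sentence follows the two enzyme-only triggers, Section 5.2.1 ties it to the elevations just described, and the combined rule has its own restart sentence. Likewise, the word recurrent suggests that recovery was assumed, but does not require it; whether an elevation that never resolved counts as recurrent is left open.

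A third reply is that the underlying omission lies in the enzyme-only triggers, so amending the restart sentence alone might change nothing for this child. That is correct, and the fix allows for it.

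**Conclusion.** The point holds as a minor gap in a safety rule. After a combined rise, a child whose ALT and AST baselines are both above 1 and up to 1.5 x ULN has no stated enzyme recovery condition, whatever the peak. Read enzyme by enzyme, the same is true for either enzyme in that band.

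Three stronger inferences are not supported:
- That no combined rise carries a recovery condition. Rises reaching 2 x ULN (normal baseline) or 3 x ULN (baseline above 1.5 x ULN) still do.
- That one enzyme in the band is enough. On the literal ALT-or-AST wording, a normal value of the other enzyme can bring in the 2 x ULN rule.
- That the 4 x ULN illustration shows a breach of a stopping rule, or a likely event. It shows only what the words do not forbid, and it would need the SRC to judge restart safe at that level.

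The conclusion assumes that the recovery sentence belongs to the enzyme-only pause. The documents do not give the baselines of the 11 enrolled children, so the number affected may be zero. SAP Section 4 records that development was stopped in July 2017, so the correction matters mainly for the protocol as written and for any reuse of these rules.

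**What to change.** Make two linked changes.

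1. In the combined-rise restart sentence of Section 6.2.1 add: *and ALT and AST have returned to baseline or study nadir, or normalized if baseline was normal*. Keep the SRC judgement and the lower dose. With recovery required first, the later permanent stop on recurrent elevation needs no new definition.
2. So that this clause operates on either reading of the trigger, do one of the following: state that the combined pause applies to any confirmed ALT or AST elevation above both baseline and ULN; or assign baselines above 1 and up to 1.5 x ULN to one of the existing enzyme-only triggers in Sections 5.2.1 and 6.2.1.

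The second option also gives this band a pause for isolated enzyme rises, which it now lacks. The choice of trigger is clinical. In this band 2B lies above 2.0 and up to 3.0 x ULN, so the permanent-stop level stays above the pause level under the 2 x ULN trigger, and sits at or below it under the 3 x ULN trigger.

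The cost is a short wording change in an amendment or site safety letter, with no new visits. The downside is a possibly longer pause for a few children.

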6.2.2 Stopping Rules for Multiple Subjects

At any time during this study, if 2 or more subjects experience the same (or similar) event considered related to SBC-103 which is either serious or severe, or any 1 subject experiences a life-threatening AE considered to be related to SBC-103, **dosing will be paused for all subjects treated at that dose or higher**. The SRC and the Sponsor will review the subject(s) data and dosing will resume only after review and agreement. Detailed information regarding the composition of the SRC, the safety data to be reviewed, and the data review process will be included in the SRC charter.

At any time during this study, the SRC or Sponsor may request a pause in dosing of all subjects based on review of reported events and all available data. Dosing will resume only after the review of data and agreement to do so by the SRC and Sponsor.

6.3 Description of SBC-103

The reference document for SBC-103 is the Investigator Brochure. SBC-103 must be administered under close supervision of the Investigator, or designee.

The study drug will be provided in a 10-mL glass vial containing approximately 10.5 mL (including 5% overfill) of a buffered solution of SBC-103 at a concentration of 2 mg/mL. The study drug contains no preservatives and vials are single use only.

6.4 Method for Assigning Subjects to Treatment Groups

In Part A, subjects will be treated sequentially as described in Section 3.1.1. In Part B, if they qualify, subjects will re-initiate treatment with SBC-103 as described in Section 6.1. In Part C, subjects will be randomized such that at least 1 subject from each cohort assigned in Part A will receive SBC-103 at 5 mg/kg and at least 1 subject from each cohort assigned in Part A will receive SBC-103 at 10 mg/kg. Thus each of the assigned dose levels from Part A will be represented in each of the 2 dose levels being studied in Part C.

6.5 Storage and Disposition of SBC-103

6.5.1 Receipt of Drug Supplies

Upon receipt of the study treatment supplies, an inventory must be performed and a drug receipt log filled out and signed by the person accepting the shipment. It is important that the designated study staff counts and verifies that the shipment contains all the items noted in the shipment inventory. Any damaged or unusable SBC-103 in a given shipment will be documented in the

Page 77 of 121

study files. The Investigator must notify study Sponsor of any damaged or unusable study treatments that were supplied to the Investigator's site.

6.5.2 Storage

All SBC-103 vials must be stored at a controlled temperature of 2-8°C. Vials should not be frozen and should be protected from light during storage.

The infusion bag or syringe containing SBC-103 diluted in 0.9% saline should be prepared immediately before infusion. Dilution should occur under controlled and validated aseptic conditions. The prepared diluted infusion bag (or syringe) may be stored at room temperature (20°C to 25°C) for no more than 8 hours, although it is preferable that prepared solution be used within 4 hours of dilution. Shaking or other forms of agitation of vials or infusion bags should be avoided. Refer to the IMP Manual for detailed instructions.

6.5.3 Disposition

The Investigator or designee (eg, a licensed pharmacist) will be responsible for maintaining accurate records for all supplies used. Opened vials of SBC-103 containing residual volume will be stored at room temperature for SBC-103 accountability. Following SBC-103 accountability, the Sponsor will provide authorization to the Investigator to return or destroy any remaining investigational product as instructed.

Under no circumstances will SBC-103 be used other than as directed in the protocol. Refer to the IMP Manual for additional details.

6.6 Preparation and Administration of Study Drug

6.6.1 Preparation of Study Drug

Dose preparation and administration should be performed using sterile, non-pyrogenic disposable materials including, but not restricted to syringes, needles, transfer tubing and stopcocks.

The infusion bag (or syringe) containing SBC-103 should be prepared just prior to the start of IV infusion. It is preferable that the prepared diluted infusion is used within 4 hours of dilution, although it may be stored at room temperature for up to 8 hours.

Prior to preparation of the infusion, the vials of study drug should be visually inspected. The solution should not be used if it contains foreign particulate matter or is discolored. The solution may be used if a small number of visible translucent to opalescent or white amorphous or threadlike particles are present in the vial. The contents should NOT be warmed using a microwave or other heat source. SBC-103 is a protein and should be not be shaken but should be handled and mixed gently to prevent foaming.

The subject's most recent protocol-scheduled weight measurement, rounded to the nearest 0.1 kg, will be used for calculating the volume of study drug to be withdrawn from the vial(s) to prepare the IV infusion. Study drug will be diluted in 0.9% saline for injection.

Refer to the IMP Manual for detailed instructions regarding the preparation of the IV infusion.

6.6.2 Administration of Study Drug

All infusions must be administered under close supervision of the Investigator, or designee. Study drug should not be infused with other products in the same infusion tubing, as the compatibility of SBC-103 in solution with other products has not been evaluated. It is recommended that all infusions of study drug be administered using in-line filtration with a low protein binding 0.2 micron filter.

The recommended duration of the infusion is 2 hours at a constant rate. The protocol allows for a change in rate should the patient experience an IAR. At the discretion of the investigator and in consultation with the sponsor, in circumstances such as a prior IAR or other like situations where patient safety is a concern, an extended duration of infusion or a variable rate is acceptable. If the infusion is not well tolerated, the infusion rate may be decreased or interrupted as noted in Section 7.1.3 and Section 6.2. All changes to infusion rate must be carefully recorded in the CRF, including the start and stop time of each rate change.

Refer to the IMP Manual for detailed instructions on the administration of SBC-103.

6.7 Randomization and Blinding of SBC-103

This is an open label study with no requirement for blinding.

In Part C, subjects will be randomized such that at least 1 subject from each cohort assigned in Part A will receive SBC-103 at 5 mg/kg and at least 1 subject from each cohort assigned in Part A will receive SBC-103 at 10 mg/kg. Thus each of the assigned dose levels from Part A will be represented in each of the 2 dose levels being studied in Part C. As noted in Section 1.4.1, a total of 11 subjects are enrolled in this study; 5 of these will be randomized to receive 5 mg/kg QOW and 6 will be randomized to receive 10 mg/kg QOW.

Details of the randomization will be provided in a randomization specification document, which will be maintained by the Sponsor.

6.8 Destruction of SBC-103

If any unused study drug material is remaining upon completion of the study, the material will be returned to the Sponsor or designee or destroyed only after the Sponsor or designee has performed final drug accountability and provided written authorization for the return or destruction of study drug. Refer to the IMP Manual for further instructions.

Page 79 of 121

7 ASSESSMENT OF SAFETY

The methods for collecting safety data are described below. All personnel involved with the study must ensure they are familiar with the content of this section.

7.1 Adverse Events and Laboratory Abnormalities

7.1.1 Clinical Adverse Events

An AE is any untoward medical occurrence in a subject, which does not necessarily have to have a causal relationship with the administration of a study drug. An AE can therefore be any unfavorable and unintended sign, symptom or disease temporally associated with the use of the study drug, whether or not considered related to the medicinal product. Pre-existing conditions that worsen in severity during the course of the study are to be reported as AEs.

All AEs occurring during the clinical study will be reported in the AE page of the CRF.

The Investigator will assess the severity, causality (relationship to study drug), and seriousness of each AE.

Severity: The Investigator will assess the severity of all AEs/SAEs as mild, moderate, or severe, based on the following definitions, developed from Clinical Data Interchange Standards Consortium (CDISC) Study Data Tabulation Model (SDTM) standard terminology v3.1.1).

- **Mild:** A type of AE that is usually transient and may require only minimal treatment or therapeutic intervention. The event does not generally interfere with usual activities of daily living.
- **Moderate:** A type of AE that is usually alleviated with additional specific therapeutic intervention. The event interferes with usual activities of daily living, causing discomfort, but poses no significant or permanent risk of harm to the research participant.
- Severe: A type of AE that interrupts usual activities of daily living, or significantly affects clinical status, or may require intensive therapeutic intervention.

Causality: AEs will be assessed as not related, unlikely related, possibly related, or related to study drug. Table 8 provides general guidance on the assessment of causality. For data reporting purposes, AEs assessed as not related or unlikely related will be classified as unrelated to study drug, and AEs assessed as possibly related or related will be classified as related to study drug. Assessment of causality should be based on the Investigator's medical judgment and the observed symptoms associated with the event.

Relationship to Study Drug	Criteria for Judgment
Related	Reasonable temporal relationship of the clinical event to study drug administration AND cannot be reasonably explained by other factors (such as the subject's clinical state, concomitant therapy, and/or other interventions).
Possibly Related	The temporal relationship of the clinical event to study drug administration makes causal relationship possible but not unlikely AND other drugs, therapeutic interventions, or underlying conditions do not provide a sufficient explanation for the observed event.
Unlikely Related	The temporal relationship of the clinical event to study drug administration makes causal relationship unlikely but not impossible AND other drugs, therapeutic interventions, or underlying conditions provide a plausible explanation for the observed event.
Not Related	Data are available to clearly identify an alternative cause for the reaction.

Table 8:Assessment of Causality

Seriousness: AEs will be classified as serious or non-serious according to the definitions provided below.

An SAE is any AE that is or leads to any of the following:

- Death.
- Immediately life threatening. An adverse event is considered "life threatening" if, in the view of either the investigator or Sponsor, its occurrence places the subject at immediate risk of death. It does not include an AE that, had it occurred in a more severe form, might have caused death.
- Requires in-patient hospitalization or prolongation of existing hospitalization.
- Congenital anomaly/birth defect.
- Persistent or significant disability or incapacity.
- An important medical event that may not result in death, be life threatening, or require hospitalization may be considered an SAE when, based upon appropriate medical judgment, the event may jeopardize the subject and may require medical or surgical intervention to prevent one of the outcomes listed above.

All SAEs and IARs must be reported to the Sponsor as described in Section 7.4.1.

